10.3. Prior and New Concomitant Medications and Procedures

Prior and concomitant medications and procedures will be collected from 3 months prior to screening through the patient's final study visit. In addition, a lifetime history of medications previously used for treatment of FSGS, including systemic corticosteroids or other systemic immunotherapeutic agents, will be collected. For medications, verbatim terms on eCRFs will be mapped to Anatomical Therapeutic Chemical (ATC) class and preferred name using the World Health Organization (WHO) Drug Dictionary Enhanced. For procedures, verbatim terms will be mapped to PT and SOC using MedDRA.

Pretreatment concomitant medications are those medications with start and stop dates prior to the initial dose of study medication. Prior concomitant medications are those medications started prior to and continued after the initial dose of study medication. New concomitant medications are those medications that were started after the initial dose of study medication. If it cannot be determined whether the medication was a new concomitant medication due to a partial start or stop date or if the medication is taken on the same date as the initial dose of study medication, then it will be counted as a new concomitant medication.

Similarly, prior procedures are those procedures with a start date prior to initial dose of study medication. Concomitant procedures are those procedures that were started after the initial dose of study medication.

Select pretreatment medications, including ACEIs, aldosterone blockers, aliskiren, ARBs, corticosteroids, immunosuppressive medications, diuretics, any other antihypertensives, and lipid-lowering medications will be summarized for each treatment group by WHO ATC level 2, WHO ATC level 4, and preferred name. All other pretreatment medications will be listed only.

Prior and new concomitant medications will be summarized for each treatment group by WHO ATC level 2, WHO ATC level 4, and preferred name. In addition, prior and new concomitant medications will be summarized separately. These summaries will present the number and percentage of patients using each medication. Patients may have more than 1 medication per ATC level and preferred name. At each level of patient summarization, a patient is counted once if he/she reported 1 or more medications at that level. Each summary will be ordered by descending order of incidence of ATC level and preferred name within each ATC level.

Prior and concomitant procedures will be summarized for each treatment group by SOC and PT.

10.4. Clinical Laboratory Evaluations

Laboratory parameters will be summarized in the standard international system of units. Quantitative laboratory results will be summarized by treatment group using descriptive statistics at baseline and each post-baseline scheduled visit. Both absolute and percentage change from baseline will also be summarized.

10.4.1. Shifts in Normal Range

Shift tables (ie, low-normal-high at baseline versus low-normal-high at post-baseline visit in a 3-by-3 contingency table) from baseline to worst (including scheduled or unscheduled) and last value (scheduled or unscheduled) will be provided for hematology, serum chemistry, and coagulation by treatment group. For urinalysis parameters, a shift table depicting shifts to/from positive/negative from baseline to worst and last value will be provided.

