Following a 108-week blinded treatment period, treatment with study medication will be discontinued, and patients may be evaluated for eligibility in the open-label extension using values from the Week 108 visit as screening assessments (see Section 6.2.2). At this time, the Investigator should resume standard-of-care treatment, including treatment with RAAS inhibitors provided there are no contraindications for their use. If the patient was treated with irbesartan at study entry, an alternative ARB at an equivalent dose is required from Week 108 to Week 112. The Investigator may make additional adjustments in antihypertensive medications as necessary to adequately control the patient's blood pressure.

Patients will return to the site for the final visit of the double-blind period 4 weeks after study medication has been discontinued (ie, Week 112; see Figure 1).

Figure 1: Study 021FSGS16010 Overview Flow Chart of the Double-Blind Period

^a Screening may begin after informed consent has been signed. The screening window begins on the day of the patient's first in-clinic study procedure. Patients should be screened within the 6-week screening period; however, under extenuating circumstances the screening period may be extended by a maximum of 2 weeks.

^b For patients who are undergoing washout from RAAS inhibitors.

^c Patients whose body weight is ≤ 50 kg at screening will receive one-half the otherwise specified doses of either sparsentan or irbesartan (active control). Weight will be measured at each visit and the dose increased at the Investigator's discretion if the patient's weight reaches >50 kg.

^d Day 1 events shown will occur in the order in which they are listed.

^e Randomization will be stratified by eGFR value (≥ 30 to <60 mL/min/1.73 m² and ≥ 60 mL/min/1.73 m² for all patients) and UP/C (≤ 3.5 g/g and >3.5 g/g [396 mg/mmol; patients ≥ 18 years of age] or ≤ 2 g/g and >2 g/g [226 mg/mmol; patients <18 years of age]) at screening.

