- o Dispense study medication. Note: at Visit 3, patients will be randomized via IWRS and the first dose will be administered in the clinic. Patients will be instructed to take their study medication at the clinic on the day of office visits. All other days, study medication should be taken at approximately the same time each day, preferably prior to the morning meal. Patients will be instructed to swallow the capsules whole, and not to open, break, chew, crush, or split the capsule prior to taking. Patients will also be instructed to avoid drinking or eating anything that contains grapefruit, Seville oranges (bitter oranges often used as marmalade), or starfruit (carambola) throughout the study. The patient will be instructed to bring all study medication and their original containers to the next clinic visit.

Table 5: Double-Blind Period: Schedule of Events from Week 24 Through End of the Double-Blind Period

Week	Blinded Treatment Period								End of Blinded Treatment ^k
	Week 24	Week 36	Week 48	Week 60	Week 72	Week 84	Week 96	Week 108 ^j / EOT/ET	Week 112
Visit	9	10	11	12	13	14	15	16	17
Visit Window	± 7 days	± 7 days	± 7 days	± 7 days	± 7 days	± 7 days	± 7 days	± 7 days	-7 to +14 days
Physical Examination ^a	X	X	X	X	X	X	X	X	X
Vital Signs ^b	X	X	X	X	X	X	X	X	X
Clinical Laboratory Assessments (chemistry, hematology) ^c	X	X	X	X	X	X	X	X	X
Aldosterone, NT-proBNP, ^d Plasma Renin Activity, Endothelin		X		X		X		X	X
Biorepository Samples (blood and urine, if consented)		X		X		X		X	X
12-lead Electrocardiogram	X	X	X	X	X	X	X	X	
Quantitative Urinalysis (3 first morning voids) ^e	X	X	X	X	X	X	X	X	X
Routine Urinalysis	X	X	X	X	X	X	X	X	
PK Plasma Levels ^f	X	X	X						
QoL Questionnaire ^g	X	X	X	X	X	X	X	X	X
Urine Pregnancy Test ^h	X	X	X	X	X	X	X	X	X
Dispense Urine Pregnancy Tests ^h	X	X	X	X	X	X	X	X	X ¹
Medication Dispensing for Double-Blind Period	X	X	X	X	X	X	X		
Informed Consent for OLE									X ¹
Medication Dispensing for OLE ⁱ									X ¹
Medication Accountability	X	X	X	X	X	X	X	X	
Adverse Event Assessment	-----Continuous Monitoring -----								
Concomitant Medications/Therapies	-----3 Months Prior to Screening Followed by Continuous Monitoring -----								

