4. STUDY DESIGN

4.1. Summary of Study Design

This is a randomized, multicenter, double-blind, parallel, active-control study, with an open-label extension of up to 156 weeks, in patients with FSGS. Patients who meet inclusion criteria during screening and who are taking renin-angiotensin-aldosterone system (RAAS) inhibitors will undergo a 2-week washout period from these agents prior to randomization. Approximately 300 eligible patients will be randomized 1:1 to receive either sparsentan or an active control (irbesartan). Randomization will include stratification by screening eGFR and UP/C values. The strata will be as follow:

- eGFR strata:
 - ≥ 30 to < 60 mL/min/1.73 m² (all patients)
 - ≥ 60 mL/min/1.73 m² (all patients)
- UP/C strata:
 - ≤ 3.5 g/g (396 mg/mmol; patients ≥ 18 years of age) or ≤ 2 g/g (226 mg/mmol; patients < 18 years of age)
 - > 3.5 g/g (396 mg/mmol; patients ≥ 18 years of age) or > 2 g/g (226 mg/mmol; patients < 18 years of age)

Additional antihypertensive agents are allowed during the study to maintain blood pressure $\leq 130/80$ mmHg (patients ≥ 18 years of age) or \leq the 75th percentile (patients < 18 years of age), with the exception of those that inhibit the RAAS and endothelin systems.

Study visits in the double-blind period will be conducted at 2, 4, 6, 8, and 12 weeks after randomization and at 12-week intervals thereafter. Following the 108-week blinded treatment period, treatment with study medication will be discontinued. Patients will return to the clinical site for the final visit of the double-blind period 4 weeks after study medication has been discontinued.

Patients may be evaluated for eligibility in the open-label extension using values from the Week 108 visit (end of blinded treatment period) as screening assessments. Patients with an eGFR < 30 (but > 20) mL/min/1.73 m² will be eligible for participation in the open-label extension at the discretion of the Investigator but will require close monitoring of eGFR and serum potassium.

Open-label extension study visits will be conducted at 12-week intervals. A study visit 2 weeks after the start of the open-label extension will also be conducted to assess tolerability to sparsentan.

Patients will participate in the open-label extension for up to 156 weeks, for a total of 268 weeks in the study (ie, double-blind and open-label periods).

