10. SAFETY AND TOLERABILITY

Safety analyses will be conducted using the Safety Analysis Set at both interim and final analysis. At the interim analysis, all available data will be summarized. Unless otherwise noted, all safety analyses will be conducted using on-study data. All safety analyses specified below refer to the double-blind period only, except where noted. If >5% of patients initiate RRT while on study, select summaries excluding results after initiation of RRT may be prepared.

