10.7.1. Peripheral Edema

The presence and staging of peripheral edema will be summarized by frequency counts and percentages based on the following grade scale: 0, 1+ (trace), 2+ (mild), 3+ (moderate), and 4+ (severe), where 0 denotes no presence of edema. A shift table indicating changes in edema severity from baseline to worst (including scheduled and unscheduled), last value (scheduled and unscheduled), and at each scheduled post-baseline visit will be provided by treatment group.

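### At the final analysis, last-value laboratory and edema shifts mix on-drug and off-drug values, and the normal-range tables show no end-of-treatment status

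*SAP*

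**What the plan says.** **Data scope.** SAP 10 states: "Unless otherwise noted, all safety analyses will be conducted using on-study data". It adds: "All safety analyses specified below refer to the double-blind period only, except where noted".

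**End of the period.** Protocol 6.2.1 says: "Patients will return to the site for the final visit of the double-blind period 4 weeks after study medication has been discontinued". That visit is Week 112, and SAP 4.1 says the same. From Week 108 the investigator is to restart standard of care, including RAAS inhibitors unless contraindicated.

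**Shift rules.** SAP 10.4.1 gives normal-range shifts "from baseline to worst (including scheduled or unscheduled) and last value (scheduled or unscheduled) will be provided for hematology, serum chemistry, and coagulation" and nothing by visit. SAP 10.4.2 (CTCAE grade) and 10.7.1 (edema) also give worst and last value, but add by-visit shifts. For edema the wording is "last value (scheduled and unscheduled), and at each scheduled post-baseline visit will be provided by treatment group".

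**Schedule.** In Protocol Table 5 the row beginning "Clinical Laboratory Assessments (chemistry, hematology" and the physical examination row, which includes edema, are both marked at Week 112. The row "Routine Urinalysis" stops at Week 108. Table 4 schedules prothrombin time and INR at screening only.

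**Patients who stop early.** Protocol 6.4.2 encourages those who stop drug to keep attending through Week 112. Protocol 6.5 asks for early-termination assessments close to the last dose in those who leave the study.

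**On-treatment limits.** SAP 6.5.4 and 8.1 set one for efficacy. SAP 10.1.3 sets one for selected adverse event summaries. None is set for laboratory or edema shifts.

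**The concern.** A shift to last value in a safety report is easily taken as the patient's status at the end of treatment. Here, for most patients who complete, it would be their status after stopping. The two arms are then compared when neither is on randomized drug and many patients in both are back on RAAS inhibition.

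The efficacy plan keeps these situations apart: eGFR at Week 112 is its own post-cessation endpoint. The laboratory and edema shifts do not.

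The affected data bear on safety topics that the documents name: hyperkalemia and edema in Protocol 4.1, and hepatic, fluid-retention and anemia topics in SAP 10.1.2. If such an effect eases after the drug stops, the last-value column shows less of it than existed on drug.

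**Working it through.** **1. The plan's own interval.** SAP Table 2 gives target days 757 (Week 108 = 108 × 7 + 1) and 785 (Week 112 = 112 × 7 + 1). 785 − 757 = 28 days, which reproduces the stated 4 weeks. The laboratory column of Table 2 is headed for eGFR and safety labs, so Week 112 is an analysis visit for safety laboratory data.

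**2. Spread for completers.** The visit windows are ±7 days at Week 108 and −7 to +14 days at Week 112 (Protocol Table 1).
- Week 112 window counted from the actual Week 108 visit: 28 − 7 = 21 to 28 + 14 = 42 days.
- Both windows counted from Day 1: (785 − 7) − (757 + 7) = 14 to (785 + 14) − (757 − 7) = 49 days.

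**3. Early stoppers who attend Week 112.** Weeks off drug = 112 − week of last dose. A last dose at Week 96 gives 16 weeks, Week 60 gives 52, Week 36 gives 76, Week 12 gives 100 and Week 2 gives 110.

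**4. Patients who leave the study.** Their last value is the early-termination assessment, near the last dose. So one column holds values from about zero to about 110 weeks off drug.

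**5. Which tables are affected.** Chemistry, hematology and edema are. For a completer the scheduled routine urinalysis ends at Week 108, so that shift is unaffected. Coagulation has no scheduled post-baseline sample, so the scheduled Week 112 visit does not affect it.

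**6. Where on-drug status is still shown.**

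| Output | Worst | Last | By visit |
|---|---|---|---|
| Normal-range shift (10.4.1) | yes | yes | no |
| CTCAE shift (10.4.2) | yes | yes | yes |
| Edema shift (10.7.1) | yes | yes | yes |
| Descriptive laboratory summaries (10.4) | – | – | yes |

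Table 2 also separates Week 108 (Days 716–771) from Week 112 (after Day 771) in the by-visit laboratory output. Only the normal-range shift lacks an end-of-treatment view.

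**7. Illustration, on assumptions that are not in the documents.** Let c be the share completing treatment and f the share of early stoppers who stay in follow-up, equal in both arms, with all completers attending Week 112. The share of last values near the last dose is s = (1 − c)(1 − f).
- With c = 0.80 and f = 0.50: s = 0.20 × 0.50 = 0.10.
- With c from 0.60 to 0.90 and f from 0.30 to 0.80: s runs from 0.10 × 0.20 = 0.02 to 0.40 × 0.70 = 0.28.

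Suppose a 10-point on-drug excess of which a fraction r reverses. The column shows 10 × [s + (1 − r)(1 − s)].
- r = 1: 1.0 point (0.2 to 2.8).
- r = 0.5: 10 × (0.10 + 0.45) = 5.5 points (5.1 to 6.4).
- r = 0: 10 points, no loss.

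**The case against.** The strongest reply is that on-drug effects are not hidden. The 10.4.1 sentence itself includes a shift to worst value, scheduled or unscheduled, which captures an abnormality that later resolves. By-visit summaries, CTCAE and edema shifts, liver-test thresholds (10.4.3) and on-treatment adverse event summaries all remain. No test or decision rule uses the last-value column. All of this stands, and it limits the point to one column plus one missing table.

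A second reply is that last on-study value is a legitimate choice, because it shows whether an abnormality persisted, and that the SAP never calls it end-of-treatment status. This is fair as far as it goes. But the column does not answer the persistence question cleanly either, because time off drug differs so widely between patients. At the interim analysis SAP 10 uses all available data, so patients still on treatment give on-drug last values. The same label therefore means different things at the two analyses.

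Some stronger readings are tempting but unsupported:
- A reader might infer that every Week 112 attendee is about 4 weeks off drug. That fits treatment completers only.
- A reader might infer that last-value ECG shifts are all on drug because ECG stops at Week 108. Early stoppers who keep attending have off-drug ECGs too.
- A reader might infer that drug effects are washed out. The documents give no reversal times, and with RAAS inhibitors resumed Week 112 is not a treatment-free visit.

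**Conclusion.** The point holds in limited form. At the final analysis, the last-value shifts for chemistry, hematology and edema are off-drug values for completers who attend Week 112: 28 days at target, 14 to 49 days across the windows. For early stoppers followed to Week 112 they can be months to about 2 years off drug. For patients who leave the study they are near the last dose.

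The column would understate any effect that reverses on stopping. The amount depends on completion, follow-up and reversal rates that the documents do not give, so the figures in step 7 show scale only. The firm gap is in SAP 10.4.1, where no normal-range shift shows end-of-treatment status.

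The reading rests on on-study data including Week 112. The SAP does not define the term, but its scope sentence, its visit table and its separation of on-study from on-treatment adverse events in 10.1.2 all point that way. This is a descriptive safety table; the efficacy conclusions are not affected.

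**What to change.** In SAP 10.4.1, 10.4.2 and 10.7.1:
- Report the shift to the last on-treatment value: the last value up to the last randomized dose plus a short window fixed in advance for safety assessments. The Week 108/EOT visit counts only if it falls inside that window; otherwise off-drug Week 108 values from early stoppers would re-enter.
- Label the existing column as last on-study value, or show Week 112 separately.
- Add a by-visit shift to 10.4.1, at least at Week 108.

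The window needs its own definition. The 3 days in SAP 8.1 is written for efficacy. The adverse event rule in 10.1.3 allows 30 days after early discontinuation and, for completers, runs to the first open-label dose, so carried over to laboratory data it would count Week 112 as on treatment. Taking the last dose at the Week 108 visit, any window shorter than 14 days keeps Week 112 out even at the smallest gap in step 2.

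The cost is SAP wording and one more column or table. No new data and no protocol amendment are needed.

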10.4.2. Shifts in CTCAE Toxicity Grade

Shifts in Common Terminology Criteria for Adverse Events (CTCAE) toxicity grade of laboratory tests from baseline to worst value (scheduled or unscheduled), last value (scheduled or unscheduled), and at each scheduled post-baseline visit will be provided by treatment group. The toxicity grades are in the CTCAE Version 4.03.

Summaries will present the number and percentage of patients with shifts in laboratory toxicity grade by treatment group.

10.4.3. Incidence of Liver Function Abnormalities

The incidence of patients with abnormalities in liver function tests (ALT, AST, alkaline phosphatase [ALP], and total bilirubin) will be summarized overall for the following categories:

- ALT and AST:
 - $>1 \times \text{ULN}$
 - $>2 \times \text{ULN}$
 - $>3 \times \text{ULN}$
 - $>5 \times \text{ULN}$
 - $>8 \times \text{ULN}$
- ALP:
 - $>1 \times \text{ULN}$
 - $>1.5 \times \text{ULN}$
 - $>2.5 \times \text{ULN}$
 - $>5 \times \text{ULN}$

- Total bilirubin:
 - $>1 \times \text{ULN}$
 - $>1.5 \times \text{ULN}$
 - $>2 \times \text{ULN}$
 - $>3 \times \text{ULN}$

Scatterplots of ALT versus AST, ALT versus total bilirubin, and AST versus total bilirubin maximum post-baseline values will be presented. If appropriate, evaluation of drug-induced serious hepatotoxicity plots of ALT or AST $>3 \times \text{ULN}$ accompanied with total bilirubin by treatment group will be presented for assessment of potential drug-induced liver injury. A listing of patients with $>2 \times \text{ULN}$ total bilirubin and $>3 \times \text{ULN}$ ALT or AST at any time on study will be provided.

10.4.4. Incidence of Clinically Significant Local Labs

The incidence of patients with clinically significant local labs will be summarized by treatment group and overall at each baseline and post-baseline visit for each local lab parameter collected. Percentage will be based on the number of patients with local lab results for each parameter and visit.

10.5. Vital Signs

The results and change from baseline to each post-baseline scheduled visit will be summarized for blood pressure (systolic and diastolic), heart rate, respiration rate, temperature, and weight.

The number and percentage of patients meeting the following criteria at any time during the study will also be summarized:

- Systolic Blood Pressure:
 - ≤ 100 mmHg
 - A decrease from baseline more than 30 mmHg
 - >180 mmHg
 - An increase from baseline more than 40 mmHg
- Diastolic Blood Pressure:
 - ≤ 60 mmHg
 - A decrease from baseline more than 20 mmHg
 - >105 mmHg
 - An increase from baseline more than 20 mmHg
- Heart Rate:
 - <45 beats per minute
 - A decrease from baseline more than 20 beats per minute

- >120 beats per minute
- An increase from baseline more than 20 beats per minute

For the analysis of orthostatic hypotension, the number and percentage of subjects with >20 mmHg decrease in systolic blood pressure at any time and the number and percentage of subjects with >10 mmHg decrease in diastolic blood pressure at any time will be presented.

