7.1. Criteria for the Study

7.1.1. Inclusion Criteria

A patient will meet all of the following criteria to be eligible for this study.

1. The patient or parent/legal guardian (as appropriate) is willing and able to provide signed informed consent, and where required, the patient is willing to provide assent, prior to any screening procedures.
2. The patient has biopsy-proven FSGS lesion(s) or documentation of a genetic mutation in a podocyte protein associated with FSGS. The biopsy may have been performed at any time in the past. The patient will be enrolled based on light microscopy diagnosis of FSGS and supportive findings on either electron microscopy (EM) or immunofluorescence (IF) analysis (preferably both). In exceptional cases, the patient may be enrolled based on light microscopy diagnosis of FSGS lesion(s) in the absence of EM or IF analysis, provided the history and/or the course of the disease are indicative of primary FSGS and the case has been reviewed by the Medical Monitor and Investigator.
3. Sites within the US and UK: The patient is male or female aged 8 to 75 years, inclusive, weighing ≥ 20 kg, at screening.
Sites outside the US and UK: The patient is male or female aged 18 to 75 years, inclusive, weighing ≥ 20 kg, at screening.
4. The patient has a UP/C ≥ 1.5 g/g (170 mg/mmol) at screening.
5. The patient has an eGFR ≥ 30 mL/min/1.73 m² at screening.

6. The patient has a mean seated blood pressure $\geq 100/60$ mmHg and $\leq 160/100$ mmHg (patients ≥ 18 years of age) or between the 5th and 95th percentile for age, sex, and height (patients < 18 years of age; [Banker 2016](#)).

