titrating up to the target dose; tolerance is defined as blood pressure measurements >100/60 mmHg (patients ≥18 years of age) or above the 5th percentile for sex and height (patients <18 years of age; [Banker 2016](#)) after 2 weeks and no adverse events (AEs) or laboratory findings interfering with the patient’s continuation on study medication. Patients who display asymptomatic blood pressure values ≤100/60 mmHg (patients ≥18 years of age) or ≤90/50 mmHg or below the 5th percentile for sex and height (whichever is lower in patients <18 years of age), or who present with clinical symptoms of orthostatic hypotension but otherwise tolerate the initial dose will continue after the Week 2 visit without titrating up to the target dose. At the Investigator’s discretion and in consultation with the Medical Monitor, patients weighing >50 kg who do not tolerate the initial dose for any reason (including changes in laboratory parameters assessed at Week 2) may continue at one-half the initial dose. Patients weighing ≤50 kg who do not tolerate the initial dose for any reason (including changes in laboratory parameters assessed at Week 2) will be discontinued from the study.

The Week 2 PK sample will be drawn prior to escalating the patient to the target dose.

Dose modification is permitted as presented in [Section 8.3.2](#).

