8.3.2. Dose Modification, Reduction, or Discontinuation

Patients who display asymptomatic blood pressure values $\leq 100/60$ mmHg (patients ≥ 18 years of age) or $\leq 90/50$ mmHg or are below the 5th percentile for sex and height (whichever is lower in patients < 18 years of age), or who present with clinical symptoms of orthostatic hypotension (see [Section 9.6](#)) but otherwise tolerate the initial dose will continue after the Week 2 visit (or the Week 114 visit for the open-label extension) without titrating up to the target dose. Patients who do not titrate up to the target dose at Week 2 (or Week 114) may titrate up to that dose at any time, based on evaluation of the Investigator, in consultation with the Medical Monitor as needed. Reductions from the target dose back to the initial dose are permitted at any time after titrating up to the target dose.

Patients weighing > 50 kg at screening who do not tolerate the initial dose for any reason may continue at one-half the initial dose at the Investigator's discretion and in consultation with the Medical Monitor, as needed. Patients weighing ≤ 50 kg at screening who do not tolerate the initial dose for any reason will be discontinued from the study.

In patients with temporary dose interruptions, treatment should be resumed whenever possible (including between visits), and treatment resumption should be considered at every visit following study medication interruption.

Doses may be modified at any time throughout the open-label extension for safety/tolerability reasons at the Investigator's discretion. In addition, after titration to the target dose for the open-label extension, increases above the target doses of 200 mg or 400 mg sparsentan may be considered for patients who, in the Investigator's opinion (and following consultation with the Medical Monitor), would benefit from an increased dose.

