12.8.1. Physical Examination and Vital Signs

The number and percentage of patients with physical examination abnormalities at each visit will be summarized and presented for each body system. A listing of abnormalities will also be provided.

The presence and staging of edema will be summarized by frequency counts and percentages based on semi-quantitative (0, 1+, 2+, 3+, 4+) evaluation of physical examination findings. A shift table indicating changes in edema from baseline to each post-baseline visit will be provided.

Vital signs data will be summarized as changes from baseline and will be classified as low, normal, or high based on reference ranges prespecified in the SAP. Vital sign abnormalities for each treatment will be summarized using shift tables.

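### SAP 10.5 counts low and high blood pressure with one set of fixed cut-offs at all ages, although the protocol judges patients under 18 by percentile, and it omits the reference ranges and shift tables the protocol assigns to it

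*SAP*

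**What the plan says.** SAP 10.5 introduces its threshold counts with: "The number and percentage of patients meeting the following criteria at any time during the study will also be summarized". The blood-pressure criteria are systolic ≤100 or >180 mmHg and diastolic ≤60 or >105 mmHg. There are also change criteria: for systolic, "A decrease from baseline more than 30 mmHg" and "An increase from baseline more than 40 mmHg"; for diastolic, a fall or a rise of more than 20 mmHg. No age group is mentioned.

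At US and UK sites, Protocol 7.1.1 reads: "The patient is male or female aged 8 to 75 years, inclusive, weighing ≥ 20 kg, at screening". For patients under 18 the same section requires blood pressure "between the 5th and 95th percentile for age, sex, and height". Protocol 8.1.1 defines tolerance as "blood pressure measurements >100/60 mmHg (patients ≥18 years of age) or above the 5th percentile for sex and height", the percentile applying to patients under 18. Protocol 8.1.1 and 8.3.2 hold titration in these patients at ≤90/50 mmHg or "below the 5th percentile for sex and height (whichever is lower in patients" under 18); the adult figure is ≤100/60.

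Protocol 12.8.1 adds that vital signs "will be classified as low, normal, or high based on reference ranges prespecified in the SAP", with abnormalities shown in shift tables.

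**The concern.** The SAP's low cut-offs are the protocol's adult figures, applied to patients whom the protocol judges on another scale. The table then mixes two things: readings that the protocol itself would treat as low, and paediatric readings that it would not necessarily treat so.

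This matters because low blood pressure is a named issue for this drug. Protocol 4.1 lists syncope from the antihypertensive effect as a risk, Section 4 reports hypotension among the most common adverse events in the Phase 2 study, and SAP 10.1.2 makes hypotension a safety topic of interest. The classification the protocol promised, with ranges that could have been age-specific, is not in the SAP. SAP 5.4 declares only one departure from the protocol (Amendment 6), and it concerns the surrogate endpoint.

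**Working it through.** The documents give no figure that depends on these cut-offs, so there is nothing to reproduce. The limits side by side (mmHg):

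| | Protocol, ≥18 | Protocol, <18 | SAP 10.5, all ages |
|---|---|---|---|
| Entry (7.1.1) | 100/60 to 160/100 | 5th to 95th percentile | – |
| Tolerance (8.1.1) | >100/60 | above 5th percentile | – |
| Titration hold (8.1.1, 8.3.2) | ≤100/60 | lower of 90/50 and 5th percentile | – |
| Target (6.2.1) | ≤130/80 | ≤75th percentile | – |
| Low count | – | – | ≤100; ≤60 |
| High count | – | – | >180; >105 |
| Change count | – | – | fall >30/20; rise >40/20 |

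**Low side.** Because the lower of two values applies, the hold figure under 18 is at most 90 systolic and 50 diastolic. The SAP flags ≤100 and ≤60. Readings of 91–100 systolic or 51–60 diastolic are therefore counted as low by the SAP yet lie above the hold figure. This needs no outside data.

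**High side.** A child is counted as high only above 180/105 or after a rise of more than 40/20. No criterion refers to the 95th percentile used at entry or the 75th used as target. The documents contain no percentile values. If a child's 95th percentile were 110–140 systolic (assumption), the distance to 180 would be 180 − 140 = 40 to 180 − 110 = 70 mmHg.

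**Baseline.** Adults may enter at exactly 100/60, and the SAP counts ≤100 and ≤60. The phrase on timing does not clearly exclude baseline, so such a patient may be counted without any change.

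**Missing content.** SAP 10.5 has no low/normal/high classification and no shift table for vital signs. The SAP does plan shift tables for laboratory results (10.4.1), ECG (10.6) and edema (10.7.1). The age subgroup in SAP 8.3 covers adverse events among the safety data, not vital signs.

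**Size, illustration only.** The one paediatric share given is from the Phase 2 study: 23/109 = 21%, ages 8 to 18. For shares of 5% to 21% (assumption), 300 × 0.05 = 15 to 300 × 23/109 = 63 patients. Assume child systolic readings are normal with mean 100–120, SD 8–12, within-child correlation 0.5–0.8, and 14 post-baseline visits (Weeks 2 to 112).

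- Single reading ≤100: Φ((100.5 − mean)/SD), from 1% (mean 120, SD 8) to 52% (mean 100).
- At least one reading ≤100 (simulated): 4% to 95% of children.
- At least one reading ≤100 but never ≤90 (simulated): 4% to 56%.

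The width of these ranges shows that the documents do not fix the size.

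**The case against.** The strongest reply is that this is a descriptive table with no test, alpha or decision rule attached, applied identically in both randomized arms. Other outputs also carry the signal: blood pressure and its change by visit (SAP 10.5), the repeated-measures model (8.8.5), patient listings (6.1), hypotension-associated events (10.1.2) and adverse events by age group (8.3). That stands and limits the weight of the point, but none of these gives an age-appropriate count of low readings.

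Three stronger readings are tempting and are not supported:

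- **That normal children are flagged as low.** The documents show only that flagged children can be above the hold figure. A child at 95 systolic might still be below the 5th percentile and so fail the tolerance definition; without chart values this cannot be settled. Nor does the protocol use percentiles everywhere: the orthostatic criteria in 9.6 are fixed at all ages.
- **That hypertensive children are missed.** The >180/105 cut-off matches no adult limit in the protocol. It also omits adults at 161–180/101–105, above the entry maximum. It marks extreme values at every age, and rises over 40/20 are counted in children too.
- **That the contrast between arms is diluted by a known amount.** Take assumed adult rates of 30% and 15% (ratio 2.0), with the same child flag rate in both arms. At 5% children and 35% flagged, the ratio is (0.95×0.30 + 0.05×0.35)/(0.95×0.15 + 0.05×0.35) = 0.3025/0.1600 = 1.89. At 20% and 77%, it is (0.80×0.30 + 0.20×0.77)/(0.80×0.15 + 0.20×0.77) = 0.394/0.274 = 1.44. Every input is assumed, including no drug effect on children's readings. This is a direction, not an estimate.

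**Conclusion.** The point holds on the low side and on the missing protocol content. One rule at all ages counts children at 91–100 systolic or 51–60 diastolic as low although they are above the protocol's hold figure. The ranges and shift tables that Protocol 12.8.1 leaves to the SAP are absent and not declared as a departure. On the high side only a narrower statement is supported: no absolute criterion relates a child's reading to the protocol's upper percentile. The baseline question is one of unclear wording and concerns adults as well.

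The effect is misclassification in the paediatric part of a descriptive safety table, not a demonstrated bias between arms. Efficacy, alpha and power are untouched. Its size cannot be computed, because neither the paediatric share of this trial nor the children's blood-pressure distribution is given. It is worth correcting, since the table bears on a named risk and the data are already collected.

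**What to change.** In SAP 10.5:

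1. Present the blood-pressure counts separately for patients under 18 and from 18, fixing the group by age at consent as in SAP 6.5.1. Patients who turn 18 on study then stay in one group.
2. For patients under 18, classify readings against the percentile chart the protocol already cites. First reconcile its basis: Protocol 7.1.1 refers to age, sex and height, whereas 8.1.1 and 8.3.2 refer to sex and height only.
3. State that counts use post-baseline readings only.
4. Add the low/normal/high shift table from Protocol 12.8.1 with age-appropriate ranges. It also shows who was already low at baseline.

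This concerns how readings are summarised; no dosing or other clinical rule is changed or proposed. The cost is SAP wording and a percentile lookup: age and sex are collected, and height is measured every six months under 18. One drawback is that high counts in children and adults would rest on different scales, so they should not be pooled.
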